10.9 NON-EVALUABLE

In a patient who does not have evidence of PD, the occurrence of any of the following conditions indicates a response status of NE:

- There are no images or inadequate or missing images
- Images of the liver and spleen are missing at that time point (with the exception that absence
 of splenic images will not result in an NE designation in a patient known to have undergone
 splenectomy).

Note: A time-point will be considered to have a response of NE if any target lesion is missing. PD may be assigned at any time point regardless of the extent of missing target or non-target lesions. Missing non-target lesions will not impact the ability to assess for response or disease progression.

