10.3.3 NON-TARGET LESIONS

Any other measurable and abnormal nodal lesions not selected for quantitation as target lesions may be considered non-target lesions. In addition, non-measurable evidence of CLL such as nodal lesions with both diameters <1.0 cm, extra-nodal lesions, bone lesions, leptomeningeal disease, ascites, pleural or pericardial effusions, lymphangitis of the skin or lung, abdominal masses that are not confirmed and followed by imaging techniques, cystic lesions, previously irradiated lesions, and lesions with artifacts may be considered as non-target disease.

The presence or absence of non-target disease should be recorded at baseline and at the stipulated intervals during treatment. If present at baseline, up to 6 non-target lesions should be recorded. The non-target disease at baseline will be used as a general reference to further characterize regression or progression of CLL during assessments of the objective tumor response during treatment. Measurements are not required and these lesions should be followed as "present" or "absent".

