10.5 COMPLETE RESPONSE

To satisfy criteria for a CR, all of the following criteria must be met:

- No evidence of new disease
- ALC in peripheral blood of <4 x 10⁹/L
- Regression of all target nodal masses to normal size ≤1.5 cm in the LD
- Normal spleen and liver size
- Regression to normal of all nodal non-target disease and disappearance of all detectable
- non-nodal, non-target disease
- Morphologically negative bone marrow defined as <30% of nucleated cells being lymphoid cells and no lymphoid nodules in a bone marrow sample that is normocellular for age
- Peripheral blood counts meeting all of the following criteria:
 - \circ ANC >1.5 x 10⁹/L without need for exogenous growth factors (e.g., G-CSF)
 - Platelet count \geq 100 x 10 9 /L without need for exogenous growth factors
 - o Hemoglobin ≥110 g/L (11.0 g/dL) without red blood cell transfusions or need for exogenous growth factors (e.g., erythropoietin)

Patients who fulfill all the criteria for a CR (including bone marrow criteria) but who have a persistent anemia, thrombocytopenia, or neutropenia or a hypocellular bone marrow that is related to prior or ongoing drug toxicity (and not to CLL) will be considered as a CR with incomplete marrow recovery (CRi).

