10.6 PARTIAL RESPONSE

To satisfy criteria for a PR, all of the following criteria must be met:

- No evidence of new disease
- A change in disease status meeting ≥2 of the following criteria, with 2 exceptions in which only 1 criterion is needed: 1) only lymphadenopathy is present at baseline; 2) only lymphadenopathy and lymphocytosis are present at baseline. In these 2 cases, only lymphadenopathy must improve to the extent specified below:
 - o In a patient with baseline lymphocytosis (ALC ≥4 x 10^9 /L), a decrease in peripheral blood ALC by ≥50% from baseline or a decrease to <4 x 10^9 /L
 - \circ A decrease by ≥50% from the baseline in the SPD of the target nodal lesions
 - o In a patient with enlargement of the spleen at baseline, a splenomegaly response as defined in Section 10.3.2
 - o In a patient with enlargement of the liver at baseline, a hepatomegaly response as defined in Section 10.3.2
 - A decrease by ≥50% from baseline in the CLL marrow infiltrate or in B-lymphoid nodules
- No target, splenic, liver, or non-target disease with worsening that meets the criteria for definitive PD

UTX-IB-301

- Peripheral blood counts meeting 1 of the following criteria:
 - o ANC >1.5 x 10^9 /L or >50% increase over baseline without need for exogenous growth factors (e.g., G-CSF)
 - o Platelet count >100 x 10⁹/L or ≥50% increase over baseline without need for exogenous growth factors
 - o Hemoglobin >110 g/L (11.0 g/dL) or ≥50% increase over baseline without red blood cell transfusions or need for exogenous growth factors (e.g., erythropoietin)

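### Protocol 10.9's Note on missing non-target lesions conflicts with the CR criteria in 10.5 and with 10.9's own first NE condition, so CR, PR or NE is left open

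*Protocol*

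**What the plan says.** Protocol 10.9 lists conditions that make a time point without PD non-evaluable (NE). The first is "There are no images or inadequate or missing images", and it is not limited to target sites. A Note then gives two contrasting rules. For target lesions: "A time-point will be considered to have a response of NE if any target lesion is missing". For non-target lesions: "Missing non-target lesions will not impact the ability to assess for response or disease progression". The second rule has no exception for CR.

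Protocol 10.5 is conjunctive: "To satisfy criteria for a CR, all of the following criteria must be met". One item on its list is "Regression to normal of all nodal non-target disease and disappearance of all detectable" non-nodal non-target disease. Protocol 10.6 asks less for PR: "No target, splenic, liver, or non-target disease with worsening that meets the criteria for definitive PD". Protocol 10.3.3 requires the information to be collected: "The presence or absence of non-target disease should be recorded at baseline and at the stipulated intervals during treatment". Note 6 to Table 2 asks for imaging of four regions: neck, chest, abdomen and pelvis.

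Protocol 10.2 leaves the reading methods to an independent review charter, which is not among the documents. The SAP has no rule on missing non-target lesions.

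CR rate is the proportion with a best overall response of CR (Protocol 11.10.2.1.1, SAP 6.1.2.1). Under the SAP's multiplicity text (6.5 in its contents list) it is one of three secondaries tested by Hochberg if ORR is significant in the ITT population.

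**The concern.** CR is a response, so on its plain words the non-target sentence covers it. A criterion that requires lesions to have resolved cannot be verified for a lesion nobody assessed. The sentence follows directly on the target-lesion rule, so the different treatment looks intended. It suits PR, where non-target disease need only not have progressed. It does not suit CR.

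At stake is whether the CR rate has a determinate definition. Best overall response takes the best time point, so a single time point classified as CR counts, provided the marrow, blood-count, spleen and liver criteria are also met. The study is open label (SAP 3.6), so completeness of scans and of lesion recording could differ by arm. Blinded IRC reading cannot restore what was not acquired or recorded.

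**Working it through.** **Step 1. The passages side by side.** Take a time point without PD at which every CR criterion is met except that one non-target lesion present at baseline was not assessed.

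| Text applied | Result |
|---|---|
| 10.9 Note, read literally | Assessment unaffected, so CR is possible |
| 10.5 together with 10.6 | One CR criterion is unverified, so not CR; PR if the 10.6 criteria are met |
| 10.9 first NE condition, if the lesion's region was not imaged | NE |

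No text ranks these three. If every un-imaged non-target site triggered the NE condition, the Note's last sentence would have little left to govern. The NE condition also does not clearly cover a region that was imaged but whose non-target lesion was not recorded or could not be read.

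**Step 2. Which endpoints move between CR and PR.**
- ORR is CR plus PR: no change.
- DOR starts, and TTR ends, at the first CR or PR (Protocol 4.1; SAP 6.1.2.2 and 6.1.2.3): no change.
- MRD is tested in patients in PR or CR (Protocol 7.1.2): no change in who is tested.
- CR rate: changes.

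**Step 3. Size, as an illustration.** There is no plan figure to reproduce: the documents as available give no expected CR rate and no frequency of missing non-target lesions. Inputs are about 120 patients randomized 1:1 (SAP 3.6), so about 60 per arm, all assumed treated; a single stratum; and assumed CR counts. The SAP tests CR rate by CMH.

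One CR is 1/60 = 1.7 percentage points in its arm.

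With *a* CRs in one arm, *c* in the other and m = a + c, the single-stratum CMH statistic without continuity correction is

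X² = (a − m/2)² / V, where V = 60·60·m·(120 − m) / (120²·119) = m(120 − m)/476.

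| Split | m | V | X² | p |
|---|---|---|---|---|
| 6-1 | 7 | 7·113/476 = 1.662 | 2.5²/1.662 = 3.76 | 0.053 |
| 7-1 | 8 | 8·112/476 = 1.882 | 3²/1.882 = 4.78 | 0.029 |
| 5-0 | 5 | 5·115/476 = 1.208 | 2.5²/1.208 = 5.17 | 0.023 |
| 6-0 | 6 | 6·114/476 = 1.437 | 3²/1.437 = 6.26 | 0.012 |

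The Hochberg thresholds are 0.05, 0.025 and 0.0167. Adding one CR to 6-1 crosses 0.05; adding one to 5-0 crosses 0.0167. Which threshold binds depends on the DOR and TTR p-values. The 0.05 crossing decides the CR test when CR has the largest of the three p-values. The 0.0167 crossing decides it when CR has the smallest and the other two fail their thresholds.

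Protocol 11.10.1 names Fisher's exact test instead. By Fisher, 5-0 to 6-0 gives 0.057 to 0.027, which crosses 0.05; 6-1 to 7-1 gives 0.114 to 0.061, which does not.

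**The case against.** The strongest reply is that the sentence is a rule on evaluability, not a waiver of CR criteria. It sits under the NE heading and can be read as saying only that a missing non-target lesion does not by itself make a time point NE. Section 10.5 is nowhere suspended, so the unassessed lesion leaves CR unmet and the time point is PR. The charter may already say so. This reading is reasonable, and it is the one the fix adopts. It is not the only reading of an unqualified sentence, and neither the protocol nor the SAP selects it.

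Three stronger readings are tempting, and the documents do not support them.

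- A reader might infer that a scan omitting the neck or chest can plainly be called CR. Table 2 requires both regions, so such a scan has missing images and on its face meets the first NE condition in 10.9.
- A reader might infer that one incomplete scan is enough for a false CR, or that DOR and TTR would be distorted. CR also needs a low ALC, recovered blood counts, normal spleen and liver, and negative marrow (10.5), with a post-baseline biopsy to confirm it (Table 2, note 5). The DOR and TTR dates do not differ between CR and PR.
- A reader might measure the effect by moving one CR between arms, from 5-1 to 6-0 (CMH p 0.095 to 0.012). A wrongly assigned CR adds one in one arm and removes none from the other. Starting from 5-1, the comparison is 6-1: 0.095 to 0.053, not significant either way.

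**Conclusion.** The conflict is real. The Note in 10.9, the first NE condition in 10.9 and the CR criteria in 10.5 give different answers for the same time point, and no text available here chooses among CR, PR and NE. What is established is an undetermined classification rule, not that the plan authorises unverified CRs.

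The risk from a wrongly assigned CR is confined to the CR rate, which is formally tested only if ORR is significant. One such patient is worth 1.7 points in an arm. At low CR counts that can decide a Hochberg comparison, though at other counts it changes nothing. This rests on 60 per arm, a single stratum and assumed CR counts. The actual effect and its direction cannot be estimated, because the documents give neither the expected CR rate nor how often non-target lesions go unassessed. The charter, which is not available here, could narrow the gap.

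**What to change.** Replace the last sentence of the 10.9 Note with:

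> A missing non-target lesion does not by itself make the time point NE, but if any non-target lesion present at baseline is not assessed, the time-point response can be no better than PR; PR, SD and PD are assessed from the available data.

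Then state how this relates to the first NE condition when a whole required region was not imaged. Without that, the new wording would still conflict with the NE condition. The IRC charter should carry the same rule.

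The cost is one or two sentences in the protocol and a matching charter entry. The cap turns CR into PR at the affected time point, so it removes no responder from ORR. The CR rate may be slightly lower, or CR assigned later, until a complete scan is available.

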10.10 LYMPHOCYTOSIS DURING THERAPY

Upon initiation of ibrutinib, a temporary increase in lymphocyte counts (i.e., $\geq 50\%$ increase from baseline and above absolute lymphocyte count of 5,000/mcL) may occur. The onset of isolated lymphocytosis usually occurs during the first few weeks of ibrutinib therapy and usually resolves by a median of 8 weeks. Patients with lymphocytosis should be continued on study drug until the occurrence of definitive disease progression (i.e., disease progression that is manifest by worsening CLL-related signs other than lymphocytosis alone), or the occurrence of another reason to discontinue study therapy. New or increasing lymphocytosis after 6 months of starting treatment may be considered disease progression and should be confirmed as per the response criteria.

10.11 MINIMUM RESIDUAL DISEASE

In patients who achieve a PR or CR, minimum residual disease will also be assessed first by peripheral blood. If a patient is determined to be MRD negative by peripheral blood, a bone marrow aspirate will be obtained to assess MRD in the bone marrow. Patients will be defined as having a clinical remission in the absence of MRD (i.e. "MRD negative") when they have blood or marrow with less than one CLL cell per 10,000 leukocytes.

UTX-IB-301

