4.1 EFFICACY ENDPOINTS

Progression-free survival (PFS)

PFS is defined as the interval from randomization to the earlier of the first documentation of definitive disease progression or death from any cause.

Definitive disease progression based on standard criteria (Hallek et al. 2008) and occurring for any reason (i.e., increasing lymphadenopathy, organomegaly or bone marrow involvement; decreasing platelet count, hemoglobin, or neutrophil count; or worsening of disease-related symptoms) other than lymphocytosis.

Overall response rate (ORR)

ORR is defined as sum of CR and PR rates.

Duration of Response (DOR)

Defined as the interval from the first documentation of CR or PR to the earlier of the first documentation of disease progression or death from any cause.

Complete Response (CR) Rate

CR rate is defined as the proportion of patients who achieve a CR.

Minimal Residual Disease (MRD) Negativity Rate

MRD negativity rate is defined as the proportion of patients who are MRD negative, excluding any patients who remain on study treatment at the time of the analysis and have a Cycle 1/Day 1 start date less than 6 months from the time of the analyses. For the sake of clarity, the MRD negative analysis will exclude those patients that are too early to evaluate because MRD negativity is only tested for patients on study \geq 6 months. Patients who drop off study for any reason prior to their 6-month visit will be included in the analysis.

UTX-IB-301

 $\frac{\textbf{Time to Response (TTR)}}{\textbf{TTR is defined as the interval from randomization to the first documentation of CR or PR}$

UTX-IB-301 Dated: 31 July 2017 (Ver. 2.5) Patients must meet all of the following inclusion criteria and none of the exclusion criteria to be eligible for participation in this study.

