⁷ Serum virology to include HBsAg, HBc antibody and CMV. If HBcAg, HBc antibody, HCV or CMV is positive, patients must be evaluated for the presence of

⁸ Peripheral Blood sample draw (See study manual for all central lab instructions. +/- 7 day window for MRD sample). For patients MRD negative by peripheral blood, a bone marrow sample should be completed to confirm MRD negativity.

⁹ Must be obtained prior to ublituximab administration if on a day of infusion.

¹⁰ For women of child bearing potential, completed within 3 days prior to Day 1 of Cycle 1

¹² For del(13q), del(11q), del(17p), and (12)trisomy, IgHV and P53 gene mutation status in peripheral blood. Central FISH analysis can be performed on UTX-IB-301 study or the TGTX-LAB-001 screening protocol.

¹⁵ If clinically significant adverse event or abnormal result is observed that is not resolved by the end-of treatment visit, continue to monitor and record until stabilization or resolution of event

¹⁶ Patients should receive up to 150 mg on Day 1 and 750 mg on Day 2. Collect a hematology panel prior to Day 2/Cycle 1 infusion.

Ibrutinib Dose	Days 1 – 28 (Daily)	
*Randomize Days -7 to 0		

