11.10.2.1.4 MINIMAL RESIDUAL DISEASE NEGATIVITY RATE

The MRD negativity rate is defined as the proportion of patients who are MRD negative post-baseline. MRD negativity rate is defined as the proportion of the patients in the Treated Population who are MRD negative, excluding any patients who remain on study treatment at the time of the analysis and have a Cycle 1/Day 1 start date less than 6 months from the time of the analyses. For the sake of clarity, the MRD negative analysis will exclude those patients that are too early to evaluate because MRD negativity is only tested for patients on study ≥ 6 months. Patients who drop off study for any reason prior to their 6 month visit will be included in the analysis.

The MRD negativity rate will be compared between treatment groups at the 5%, two-sided statistical significance level using the same methodology as that described in Section 11.10.1 for ORR.

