³ Physical Exam, Vital Signs, ECOG PS, Hematology and Serum Chemistry visit days have +/- 14 day window

⁴ Day 2 visit only required for patients randomized into Arm A.

⁵ Unilateral bone marrow aspirate and/or biopsy performed at investigator discretion in patients for whom assessment of extent of CLL involvement and bone marrow cellularity is important in determining eligibility. In addition, a post-baseline bone marrow biopsy should be completed to confirm potential CR by radiological assessment.

⁶ Scans for screening should be completed within 30 days prior to Day 1 of Cycle 1. Response tumor evaluations have a +/- 7 day window. Radiology assessment should include CT or MRI imaging of neck, chest, abdomen, and pelvis.

7 Serum virology to include HBsAg, HBc antibody and CMV. If HBcAg, HBc antibody, HCV or CMV is positive, patients must be evaluated for the presence of

DNA/PCR

⁸ Peripheral Blood sample draw (See study manual for all central lab instructions. +/- 7 day window for MRD sample). For patients MRD negative by peripheral blood, a bone marrow sample should be completed to confirm MRD negativity.

⁹ Must be obtained prior to ublituximab administration if on a day of infusion.

 $^{^{10}}$ For women of child bearing potential, completed within 3 days prior to Day 1 of Cycle 1

¹¹ IgA, IgE, IgG, IgM

¹² For del(13q), del(11q), del(17p), and (12)trisomy, IgHV and P53 gene mutation status in peripheral blood. Central FISH analysis can be performed on UTX-IB-301 study or the TGTX-LAB-001 screening protocol.

¹⁵ If clinically significant adverse event or abnormal result is observed that is not resolved by the end-of treatment visit, continue to monitor and record until stabilization or resolution of event

¹⁶ Patients should receive up to 150 mg on Day 1 and 750 mg on Day 2. Collect a hematology panel prior to Day 2/Cycle 1 infusion.

Ibrutinib Dose	Days 1 – 28 (Daily)	
*Randomize Days -7 to 0		

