6.1.2.4 MINIMAL RESIDUAL DISEASE NEGATIVITY RATE

MRD negativity rate is defined as the proportion of patients in the Treated Population who are MRD negative, excluding any patients who remain on study treatment at the time of the analysis and have a Cycle 1/Day 1 start date less than 6 months from the time of the analyses. For the sake of clarity, the MRD negative analysis will exclude those patients that are too early to evaluate because MRD negativity is only tested for patients on study \geq 6 months. Patients who drop off study for any reason prior to their 6 month visit and do not have an MRD assessment will be included in the analysis and considered non-responders.

For each treatment group, the number of patients achieving MRD negativity will be divided by the total number of eligible patients (see above paragraph) to yield the proportion responding. The MRD negativity rate will be compared between treatment groups at the 5%, two-sided statistical significance level using the same methodology described in Section 6.1.1.

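### Read literally, Protocol 10.11 scores a blood-negative, marrow-positive patient as MRD negative, against the stated purpose of the marrow sample; the MRD denominator also depends on staying on treatment

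*Protocol*

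**What the plan says.** **Numerator.** Protocol 10.11 assesses MRD in patients with PR or CR, in peripheral blood first. If blood is negative, "a bone marrow aspirate will be obtained to assess MRD in the bone marrow". The same paragraph then defines patients as MRD negative "when they have blood or marrow with less than one CLL cell per 10,000 leukocytes". Footnote 8 to Table 2 of Protocol section 7 describes the same sample differently: "For patients MRD negative by peripheral blood, a bone marrow sample should be completed to confirm MRD negativity". Footnote 8 to SAP Table 2 (section 3.2) repeats that purpose: "a bone marrow sample should be completed to confirm MRD negativity". SAP 6.1.2.4 and Protocol 11.10.2.1.4 use the term MRD negative without naming a specimen. Neither says how a blood-negative patient with positive or absent marrow is scored.

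**Denominator.** Protocol 4.1, Protocol 11.10.2.1.4 and SAP 6.1.2.4 define the rate "excluding any patients who remain on study treatment at the time of the analysis" whose Cycle 1 Day 1 was less than 6 months earlier. Of those who leave, Protocol 11.10.2.1.4 says: "Patients who drop off study for any reason prior to their 6 month visit will be included in the analysis". Only the SAP adds a score: such patients who "do not have an MRD assessment will be included in the analysis and considered non-responders".

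**Status of the endpoint.** "The MRD negativity rate will be compared between treatment groups at the 5%, two-sided statistical significance level" (Protocol 11.10.2.1.4; SAP 6.1.2.4 sets the same level). SAP 3.6 describes the trial as open label. The SAP's Hochberg family contains CR rate, DOR and TTR, but not MRD.

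**The concern.** A confirmatory test should be able to overturn the result it confirms. Under the literal wording of 10.11 the MRD aspirate cannot, so patients with measurable disease in marrow would be reported as MRD negative although the schedule says marrow was sampled to check exactly that. If the team does not intend the literal wording, the alternative rule is written nowhere visible. It could then be settled after results are seen, in an open-label trial, for an endpoint with its own 5% test.

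The denominator raises a second, smaller issue. Take two patients who started on the same day, less than 6 months before the cut. The one still on treatment is left out. The one who dropped off is counted and, under the SAP, scored as a non-responder if untested. The rule therefore lowers the rate more in the arm with more early drop-off, for a reason unrelated to MRD.

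**Working it through.** The visible documents give no MRD rate or power figure, so there is no planned number to reproduce.

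**1. Outcomes of the blood-first sequence (Protocol 10.11)**

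| Blood | MRD aspirate | Literal 10.11 (blood *or* marrow) | Confirmation as in footnote 8 |
|---|---|---|---|
| Positive | Not triggered | Not negative | Not negative |
| Negative | Negative | Negative | Negative |
| Negative | Positive | **Negative** | **Not negative** |
| Negative | Missing | **Negative** | **No rule stated** |

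In the literal column, status equals the blood result in every row. The rules part company in the last two rows.

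**2. Size of the numerator effect**

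- Inputs: about 120 patients, 1:1 (SAP 3.6), so 120/2 = 60 per arm.
- One discordant patient: 1/60 = 1.7 percentage points.
- With the smaller denominators of step 3 (about 53 to 56), this is 1/56 to 1/53 = 1.8 to 1.9 points.

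To illustrate, assume blood-negative rates of 30% and 5%, equal discordance d in both arms, and 60 per arm. The confirmed rate is the blood-negative rate x (1 - d). Power is the normal approximation for two proportions at two-sided 5%.

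| d | Confirmed rates | Power |
|---|---|---|
| 0% | 30.0% v 5.0% | 96% |
| 10% | 27.0% v 4.5% | 93% |
| 30% | 21.0% v 3.5% | 84% |
| 50% | 15.0% v 2.5% | 68% |

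Every rate in this table is an assumption. Discordance that differs by arm could move the comparison either way.

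**3. Size of the denominator effect**

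Inputs from the documents: ORR analysis after at least 16 weeks = 112 days (SAP 3.5.1); accrual over 18-24 months (Protocol 6.3), taken as uniform; 60 per arm. Six months is taken either as six 28-day cycles (168 days) or as calendar months (182.6 days).

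I is the number per arm who started under 6 months before the cut: I = (days in 6 months - 112)/30.44 x 60/accrual months.

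- Six cycles: 56/30.44 = 1.84 months. I = 1.84 x 60/24 = 4.6, or 1.84 x 60/18 = 6.1.
- Calendar: 70.6/30.44 = 2.32 months. I = 2.32 x 60/24 = 5.8, or 2.32 x 60/18 = 7.7.

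Assumptions: the same MRD rate r (20% to 50%) in both arms among the M = 60 - I patients with at least 6 months; 5% of recent starters off study and untested in one arm, 20% in the other.

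Spurious difference = rM/(M + 0.05 I) - rM/(M + 0.20 I)

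| 6 months as | r | I | Rate at 5% off | Rate at 20% off | Difference |
|---|---|---|---|---|---|
| Six cycles | 20% | 4.6 | 19.92% | 19.67% | 0.2 points |
| Six cycles | 50% | 6.1 | 49.72% | 48.89% | 0.8 points |
| Calendar | 20% | 5.8 | 19.89% | 19.58% | 0.3 points |
| Calendar | 50% | 7.7 | 49.63% | 48.56% | 1.1 points |

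If every patient started at least 6 months before the cut, I = 0 and the difference is zero.

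**The case against.** The best defence of the plan is that 10.11 is the definition and footnote 8 only a sampling note, whose marker is also attached to serum chemistry in the table. On that view 10.11 is a complete blood-based rule with marrow as added information, which is a legitimate endpoint. The word *or* could also simply set the threshold for whichever specimen is tested, rather than combine two results. Both readings are possible. The first leaves the footnote's confirmatory purpose without effect; the second leaves the discordant patient unscored. Neither removes the need to reconcile the two texts.

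Three stronger inferences are not supported:

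- *Every patient with a marrow sample is already MRD negative.* Footnote 5 separately calls for a post-baseline marrow biopsy to confirm a potential CR, whatever the blood MRD result. The point concerns only the aspirate triggered by negative blood.
- *No scoring rule exists anywhere.* Footnote 8 refers to a study manual, and SAP entries between 6.2 and 6.5 cannot be read in the public copy. One can say only that no visible text settles the matter.
- *A recent starter who is off treatment but still followed is left undefined.* The sentence on patients too early to evaluate explains the exclusion and does not add a second one. Such a patient is not excluded.

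It is also fair to say that the denominator effect may be nil. The SAP is dated December 2020, its original was based on a September 2014 protocol, and accrual was planned for 18-24 months. All patients may well have passed 6 months by the cut, but the documents give no enrollment or cut-off dates.

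**Conclusion.** The conflict between Protocol 10.11 and footnote 8 is real, and the visible SAP text does not resolve it. It should be settled before lock. Its size is 1.7 points per discordant patient at 60 per arm; the number of such patients and the direction between arms cannot be determined.

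The denominator rule does condition on a post-randomization event, but it is the minor part: 0.2 to 1.1 points at the earliest cut, resting on the assumed 20% v 5% drop-off, the assumed 20-50% MRD rates and uniform accrual.

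A reader might infer that the trial's main conclusions are at risk. They are not. MRD is outside the Hochberg family, so the primary ORR test and the controlled claims on CR, DOR and TTR stand apart from it. What is exposed is the MRD comparison alone.

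**What to change.** Before database lock:

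1. In Protocol 10.11 (by clarification or a recorded change) and SAP 6.1.2.4, replace the *or* with blood negative, confirmed in marrow, for the tested endpoint. Score blood-negative patients with positive marrow as not negative, and those with missing marrow as not negative. Keep blood-only MRD as a supportive analysis and report missing marrow by arm.
2. Set the MRD denominator by Cycle 1 Day 1 date alone: at least 6 months before the cut, whatever the treatment or study status. Keep untested early drop-offs who meet that date as non-responders. State whether 6 months means six cycles or calendar months.

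The cost is wording; no new samples are needed. The MRD rate may be lower and the denominator slightly smaller. The endpoint will also depend on marrow completion, which footnote 8 words only as something that should be done, and that weighs more on the arm with more blood-negative patients. The blood-only analysis and the by-arm count of missing marrow let a reader judge that.
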